5. AMENDMENTS AND UPDATES

Substantial protocol amendments/updates so far: None

6. MILESTONES

Milestone ^a	Planned Date
Registration of protocol in the E.U. PAS register	Q3 2025
First data extraction	Q1 2026
Annual interim report #1	Q4 2026
Annual interim report #2 ^b	Q4 2027
Annual interim report #3	Q4 2028
Annual interim report #4 ^b	Q4 2029
Annual interim report #5	Q4 2030
Annual interim report #6 ^b	Q4 2031
Last data extraction	Q2 2032
Final report of study results (CSR)	Q4 2032
Registration of the results in the E.U. PAS register	To be determined

CSR=Clinical Study Report; FDA=Food and Drug Administration; PAS=post-authorization study; PSUR=Periodic Safety Update Report; Q=quarter.

^a Study progress will be provided in every PSUR.

^b Additional interim report for U.S. FDA submission only.

7. RATIONALE AND BACKGROUND

Paroxysmal nocturnal hemoglobinuria (PNH) is a rare, acquired, chronic, life-threatening blood disorder associated with anemia due to hemolysis. It is most frequently caused by a somatic mutation in the phosphatidylinositol glycan class A (PIGA) gene of hematopoietic stem cells. The onset of PNH is often insidious. Although there have been reports of spontaneous remission, the course of the disease is generally chronically progressive.

The goal of PNH therapy is to control complement-mediated hemolysis and thus counteracting anemia. Hemolysis can result in a range of debilitating consequences, such as severe fatigue, chest pain, and transfusion dependence, all of which contribute to a reduced quality of life (QoL). If left untreated, PNH can cause severe and potentially fatal complications for patients. Thrombotic events are the main cause of severe complications and death in PNH. The disorder requires life-long treatment.

PNH appears to equally affect males and females, although there may be a slight female preponderance ([NORD 2024](#)). The disorder has no clear tendency toward a specific

race or ethnicity (Shah and Bhatt 2023). PNH has an annual incidence as high as 0.6 per 100,000 persons (Farooq 2020) and its prevalence is estimated to be 1–2 per 100,000 persons in the general population (Cançado et al. 2021). In the U.S., Europe, and Japan, the overall estimated number of patients with PNH is about 10,000 (Mandala et al. 2013; Ninomiya and Okura 2022). Although patients can develop PNH at any age, the typical age of presentation is between 30 and 40 years. Children can be diagnosed with PNH, though PNH diagnosis predominantly occurs during adolescence (Curran et al. 2012; Shah and Bhatt 2023). Pregnancy-related complications are also apparent in PNH, including worsening cytopenia, thrombosis, infections, bleeding, miscarriages, and increased maternal mortality; as well as adverse fetal outcomes of fetal death and premature delivery (Alashkar et al. 2020).

The treatment options available to patients with PNH differ significantly by country and geographical region. The current standard of care (SOC) for PNH involves complement inhibition, which has significantly improved patient outcomes. Allogeneic hematopoietic stem cell transplantation (HSCT) is a curative option that is available in certain countries but presents significant risks. In countries where complement inhibitors are not currently available, management of patients is mainly through supportive care (Cançado et al. 2021).

Crovalimab, a novel, long-acting monoclonal antibody (mAb) targeting C5, has demonstrated efficacy in reducing hemolysis, improving QoL, and potentially offers a more convenient dosing schedule compared to existing therapies (eculizumab and ravulizumab). Overall, crovalimab has shown a well-tolerated safety profile, similar to that of eculizumab in patients with PNH, both in treatment naïve patients and in patients already on treatment with eculizumab or ravulizumab (Roth et al. 2025; Roth et al. 2024).

However, as crovalimab is a new treatment, comprehensive post-marketing surveillance is essential to fully understand its long-term safety profile and potential risks. This is particularly important given the chronic nature of PNH and the need for long-term treatment.

The most commonly reported adverse events (AEs) with crovalimab treatment are pyrexia, headache, infections, infusion and injection-related reactions (IRRs), injection-related reactions (only affecting crovalimab SC administration) and transient immune complex reaction (TICR), also known as Type III hypersensitivity reaction (affecting only patients switching treatments). Meningococcal infection is an important AE of crovalimab treatment, related to its mode of action.

The European Medicines Agency (EMA) and the U.S. Food and Drug Administration (FDA) have requested additional data on specific safety concerns, including:

- Serious infections: Complement inhibition can increase the risk of infections.

- Meningococcal infections: Infections caused by encapsulated bacteria are of special interest, as patients treated with the current SOC have very high-risk to encapsulate infections.
- Hemolysis after discontinuation: The potential for rebound hemolysis upon treatment cessation is high. Nevertheless, the likelihood that a patient with PNH will discontinue treatment with a complement inhibitor without switching to another similar treatment is low.
- Malignancies and hematologic abnormalities: Long-term immunosuppression may be associated with an increased risk of malignancy, including hematologic and non-hematologic malignancies.
- TICRs: Such immune reactions could occur when patients are switching from eculizumab or ravulizumab to crovalimab (and vice versa), as crovalimab and other C5 inhibitors bind to different epitopes of C5 and can form large drug-target-drug complexes (DTDCs).
- Infusion and injection-related reactions (IRRs): IRRs are considered a risk for all biologic medications, including mAbs, that are administered by intravenous (IV) and/or subcutaneous (SC) routes.
- Use in pregnancy and/or breastfeeding. The safety of crovalimab during pregnancy and breastfeeding is unknown.

To gather more information on the safety profile of crovalimab in a real-world setting, Roche has entered a partnership with the International PNH Interest Group (IPIG), to participate in the existing registry (further referred to as the “Core Registry”, ClinicalTrials.gov ID NCT06524726). A crovalimab sub-registry (further referred to as the “Crovalimab Silo” or Study MO44987) will be established, to enable additional safety data collection in patients with PNH treated with crovalimab. The study described herein (MO45473) is a secondary data use (SDU) study which aims to analyze data from the participants enrolled in the Crovalimab Silo.

8. RESEARCH QUESTION AND OBJECTIVES

8.1 RESEARCH QUESTION

The aim of this study is to characterize the safety profile of crovalimab in participants with PNH, with a specific focus on adverse events of special interest (AESIs). This study also aims to assess AEs, serious adverse events (SAEs), pregnancy, and infant outcomes in female participants with PNH exposed to crovalimab during pregnancy and through breastfeeding.

8.2 OBJECTIVES

The primary objectives for this study are as follows:

- To characterize and estimate the frequency of AESIs among participants with PNH exposed to crovalimab. AESIs are as follows:
 - Serious infections

- Meningococcal infection and other infections with encapsulated bacteria
- Development or worsening of any neurological condition (e.g., axonal neuropathy, multifocal mononeuropathy)
- Malignancies and hematologic abnormalities
- Serious hemolysis
- Transient immune complex reactions
- Infusion and injection-related reactions
- To characterize and estimate the frequency of AEs, SAEs, pregnancy outcomes, and infant outcomes in participants with PNH exposed to crovalimab during pregnancy and through breastfeeding. Specifically:
 - To estimate the frequency and further characterize all AEs, adverse pregnancy outcomes, and birth outcomes (during pregnancy until date of delivery), in pregnant female participants with PNH
 - To estimate the frequency and further characterize adverse fetal/neonatal/infant outcomes (e.g., major and minor congenital malformations, gestational age, postnatal growth and development) and SAEs at birth and through at least the first year of life of infants of mothers exposed to crovalimab during pregnancy
 - To estimate the frequency and further characterize all AEs for lactating females and infants exposed to crovalimab through breastfeeding

The secondary objectives for this study are as follows:

- To estimate the frequency and further characterize AEs and SAEs (not included as AESIs) in all participants with PNH exposed to crovalimab.
- To characterize clinical outcomes and laboratory test results relevant to PNH disease among participants with PNH who experienced an AESI
- To characterize patient-reported outcomes (PROs) among participants with PNH who experienced an AESI via a patient-reported fatigue assessment using the Functional Assessment of Chronic Illness Therapy (FACIT)-Fatigue questionnaire

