Analyses will be presented separately for the entire PNH participant cohort, pregnant female participants with PNH, all infants, and infants categorized by breastfeeding status (yes/no). When feasible, these analyses will be further detailed according to each trimester of pregnancy and each quarter within the infant's first year of development. Additionally, where data allows, outcomes will be analyzed based on prior PNH treatment and using the classifications of naïve new users and prevalent new users.

Potential confounding factors influencing safety and pregnancy outcomes, such as demographic information (e.g., age, race/ethnicity), clinical characteristics, maternal medical history, obstetrical history, comorbidities, and concomitant medications will be used in subgroup analyses among participants with PNH who experience an AESI, as well as for pregnancy or infant outcomes. Adverse events of special interest proportions and incidence rates will be compared between subgroups. Similarly, subgroup analysis by clinical and laboratory test outcomes for PNH will be performed when feasible. Safety events will be also described by causality.

Sensitivity analysis will be performed restricting the data to safety events and crovalimab exposure that was collected prospectively only. The effects of the timing of crovalimab exposure before and during pregnancy and cumulative exposure periods on each outcome will be also evaluated as sensitivity analysis. Sensitivity analysis may also include timing variations of failure to thrive (FTT) and development deficiency outcomes, when available.

Full details on all statistical analyses, including other subgroup and sensitivity analyses, will be described in the Statistical Analysis Plan (SAP).

MILESTONES

FIRST DATA EXTRACTION:

The date of first data extraction is the date when the variables used for the data analysis as per protocol are extracted for the first time. The planned first data extraction is after 6 months of Crovalimab Silo inception. The planned first data extraction is in Q1 2026.

LAST DATA EXTRACTION:

The last data extraction is the date of the end of the Crovalimab Silo registry, plus an additional 6 months to account for final data transfer. The planned last data extraction is in Q2 2032.

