Prospective data collection will commence at the initiation of treatment for participants who began therapy with crovalimab on or after the start of the Crovalimab Silo registry (illustrated as Patient A in [Figure 2](#)). For participants who began treatment with crovalimab before the Crovalimab Silo was established, retrospective data will be collected from the Core Registry into the silo, if available; while prospective data

collection will begin from the time of silo enrollment (illustrated as Patient B in Figure 2). The MAH anticipates very few cases in this last scenario.

Figure 2 Study Design for PNH in the Crovalimab Silo

IPIG = International PNH Interest Group; PNH = paroxysmal nocturnal hemoglobinuria.

The planned start date for the Crovalimab Silo refers to the date when information about the first participant in the Crovalimab Silo will be recorded in the database, which is projected to be in Q1 2026. The last data extraction and planned end of the registry, based on a planned data collection in the Crovalimab Silo, is projected in Q2 2032.

Participants' visit schedules will follow SOC. Participants' data are expected to be entered in the electronic data capture (EDC) system by the clinicians and/or their qualified designee at the time of registry enrollment and approximately every 6 months thereafter. In addition, participants and/or their parents/legally authorized representatives have the option to complete electronic patient-reported outcome (ePRO) questionnaires (i.e., the FACIT-Fatigue questionnaire) at registry enrollment, and every 6 months thereafter.

If a participant withdraws from the IPIG registry, the date and reason will be recorded in the electronic Case Report Form (eCRF), with efforts made to obtain this information. Registry site termination may happen due to inadequate participant recruitment or non-compliance with protocols, guidelines, or regulatory requirements. If a clinician withdraws, the MAH should be notified in advance, and a new clinician will be trained and identified to take over patient referrals.

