9.2.3 Participant Follow-up

The follow-up period will be the time period from index date (as defined in Section 9.2.1) until the end of the study or censoring, whichever comes first.

To evaluate AESIs and other AEs and SAEs for all participants with PNH, the date of censoring will be defined as the earliest occurrence of any of the following events:

- Consent withdrawal
- Site termination
- Crovalimab treatment discontinuation¹ (with an extra follow-up period after discontinuation)
- Enrollment into an interventional clinical trial²
- Death

To assess safety events during pregnancy and breastfeeding, including pregnancy and infant outcomes, additional censoring events will be defined:

- Date of delivery (for pregnancy safety and outcomes)
- First year of the infant's life (for safety and infant outcomes)
- On the date when breastfeeding stops or first year of the infant's life (for breastfeeding)

[figure not shown]
¹ For participants with PNH censored due to crovalimab treatment discontinuation, follow-up will continue up to 12 months if the participant does not start a new complement inhibitor or for 12 weeks if the participant starts a new complement inhibitor.

² To preserve the integrity of data collected for any interventional therapy for PNH in clinical studies, as well as to avoid duplicate safety reporting, participant data collection will be paused from the Crovalimab Silo and the Core Registry when participants enroll in an interventional clinical study for a PNH therapy.

Note: Safety events from the mother will continue to be recorded even after pregnancy ends, delivery, or the cessation of breastfeeding. Similarly, infant safety events will also continue to be recorded through their first year of age if breastfeeding is suspended.

Evaluation of pregnancy and infant outcomes during crovalimab exposure will rely on prospectively collected data within the Crovalimab Silo only for participants who enroll into the silo before being pregnant. However, for participants who enroll into the Crovalimab Silo while being pregnant, retrospective data on crovalimab exposure and outcomes will be incorporated into the silo, if such data are available from the Core Registry. Data for participants whose pregnancy outcomes occur before their enrollment in the Crovalimab Silo will not be obtainable. Very few instances are expected in these latter two scenarios due to the timing of drug approvals and site initiations in the Core Registry (see Figure 3).

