9.3.2.1.11 Congenital Malformations

Major malformations are those that have significant medical, social or cosmetic consequences, and typically require surgical intervention or are life-threatening (e.g., cleft lip, spina bifida). Minor malformations pose no significant health problem in the neonatal period and tend to have limited social or cosmetic consequences, rarely requiring surgical intervention (e.g., single palmar crease, clinodactyly). Both major and minor congenital malformations reported up to 1 year of age by the mother will be included in the analysis.

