9.5 STUDY SIZE

Enrollment will depend on the approval timelines, uptake and treatment course in each country where the sites are open, as well as the total number of evaluable participants with PNH for AESIs (described in Section 9.3.1.2). However, based on patient projections in selected countries, the MAH expects 300 participants with PNH to be enrolled with up to 7 years of follow-up during the duration of the Crovalimab Silo registry (7 years).

[Table 2](#) provides probabilities (and associated 2-sided 95% CIs) to observe at least one event for AESIs with assumed prevalence ranging from 0.5%–20% in a population of 300 participants with PNH. For example, in the crovalimab trials, 6% of patients had a serious infection, 6.4% had an injection-related reaction, and 17.8% had a TICR, while no patients presented with a meningococcal infection or a serious hemolysis (Crovalimab E.U. Risk Management Plan [RMP] Version 1.0, 28 June 2024).

Table 2 Probability to Observe at least one Event for AESIs with Varying Prevalence

Assumed Prevalence ^a	Probability to Observe at least One AESI (95% CI)
0.5%	77.8% (10.2%–99.8%)
1.0%	95.1% (46.2%–100.0%)
1.5%	98.9% (74.3%–100.0%)
2.0%	99.8% (89.1%–100.0%)
5.0%	100.0% (100.0%–100.0%)
7.0%	100.0% (100.0%–100.0%)
10.0%	100.0% (100.0%–100.0%)
15.0%	100.0% (100.0%–100.0%)
20.0%	100.0% (100.0%–100.0%)

AESI = adverse event of special interest.

Note: 95% CIs are 2-sided and were calculated using Clopper-Pearson method (Clopper and Pearson 1934).

^a Assumed prevalence obtained during whole follow-up period.

In addition, the MAH aims to enroll approximately 25 participants with PNH who are pregnant in the Crovalimab Silo registry. Nevertheless, since the management of PNH during pregnancy has been challenging and pregnancy has been discouraged in participants with PNH, there are very few reported cases of pregnant participants with PNH treated with C5 inhibitors. For example, in a similar registry, there were only 94 pregnancies in fewer than 1,086 females treated with eculizumab from June 2006 to November 2014 (Kelly et al. 2015; Höchsmann et al. 2022).

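### A full first year of infant follow-up is promised, but a fixed registry end with no latest conception or birth date cannot deliver it for late pregnancies

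*Protocol*

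**What the plan says.** - **Promise.** Section 8.2 (and the synopsis) makes it a primary objective to describe infant outcomes and SAEs "at birth and through at least the first year of life of infants of mothers exposed to crovalimab during pregnancy". Table 1 footnote h repeats the one-year minimum.
- **Outcomes that run late into that year.** Section 9.3.2.1.11: "Both major and minor congenital malformations reported up to 1 year of age by the mother will be included in the analysis". Sections 9.3.2.1.9 and 9.3.2.1.10 look at growth and development at 3, 6, 9 and 12 months where feasible. Section 9.3.2.1.15 defines infant death over weeks 12 to 52.
- **End of observation.** Section 9.2.3 stops follow-up at study end or at censoring, whichever is earlier. In section 9.1 the silo start is the date of the first recorded participant, "which is projected to be in Q1 2026", and then: "The last data extraction and planned end of the registry, based on a planned data collection in the Crovalimab Silo, is projected in Q2 2032". The synopsis instead defines the last extraction, also Q2 2032, as "the date of the end of the Crovalimab Silo registry, plus an additional 6 months to account for final data transfer", which puts registry end at about Q4 2031.
- **Eligibility.** Section 9.2.2 selects pregnancies by exposure and infants by age and breastfeeding. It gives no latest conception or birth date and no minimum observable time.
- **Size and duration.** Section 9.5: "the MAH expects 300 participants with PNH to be enrolled with up to 7 years of follow-up" over a stated 7 years, and "the MAH aims to enroll approximately 25 participants with PNH who are pregnant in the Crovalimab Silo registry". It adds that the sponsor will consider renegotiating a longer collection period if needed.
- **Analysis.** Section 9.7.1 computes incidence rates from person-time up to event or censoring. It also gives incidence proportions: the share affected by AESIs, SAEs and AEs up to the extraction date. Section 9.7.2 presents analyses separately for all infants.

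**The concern.** The one-year window and the fixed end of the registry cannot both hold for every infant. Nothing stops pregnancies from entering late, and nothing commits the registry to follow their infants after it closes. An infant born in the final 12 months is lost to view before its first birthday, and a pregnancy conceived in about the final nine months may have no outcome at the end.

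Two things are at stake. First, a primary objective describes a property that the design lacks for a noticeable share of an already small group. Second, findings that surface later in the first year (malformations not seen at birth, missed milestones, deaths after 12 weeks) will be under-counted wherever a crude proportion treats a partly observed infant as event-free. The same arises at each annual interim report. At the first one (Q4 2026, with a Q1 2026 start), no infant conceived after the mother's enrollment can have reached 12 months.

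**Working it through.** **The plan's own figures.** The protocol gives no figure for infants completing one year. Its only sample-size calculation, Table 2, concerns AESIs in 300 participants. It reproduces, for example 1 − (1 − 0.005)^300 = 77.8%, but says nothing about infants.

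**Length of collection, T.**
- Q1 2026 to Q2 2032 is 6.0 to 6.5 years; take 6.25.
- If registry end is six months before extraction, T is 5.5 to 6.0 years.
- The stated 7 years is reached only by placing inception at Q3 2025 (first extraction in Q1 2026 less six months) and the end at Q2 2032.
- The range used is therefore 5.5 to 7.0 years.

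**Latest dates for a complete first year** (12 months after birth, 9 months' gestation):
- End Q2 2032: birth by about Q2 2031, conception by about Q3 2030.
- End Q4 2031: birth by about Q4 2030, conception by about Q1 2030.

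**Share of pregnancies not followable to one year.** The protocol gives no accrual curve, so two conception patterns are assumed. The target of 25 is read as 25 pregnancies. Early losses are ignored, so these are upper-end counts for each T.

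- Evenly spread conceptions, T = 6.25: still ongoing 0.75/6.25 = 12% (3.0 of 25); infant under 12 months 1.00/6.25 = 16% (4.0 of 25); together 1.75/6.25 = 28% (7.0 of 25).
- Same pattern, T = 7.0: 1.75/7.0 = 25% (6.2). T = 5.5: 1.75/5.5 = 32% (8.0).
- Linearly rising conceptions, T = 6.25: 1 − (1 − 0.28)² = 48% (12.0). Over T = 7.0 to 5.5 the range is 44% to 54% (10.9 to 13.4).

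**Effect on a crude one-year proportion.** Assume a constant hazard through the first year, births spread evenly over L = T − 0.75 = 5.5 years, and a true one-year risk p = 10%.
- λ = −ln(0.9) = 0.1054.
- Mean risk observed in infants born in the last year: 1 − p/λ = 1 − 0.1/0.1054 = 0.051.
- Proportion over all live births: (4.5 × 0.10 + 1 × 0.051)/5.5 = 0.501/5.5 = 9.1%.
- The same calculation at p = 20% gives 18.3%.

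A milestone due at 12 months cannot be assessed at all in infants still under 12 months.

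**Why the pregnancy denominator needs care.** Admitting every pregnancy whose outcome is already known looks natural, but near a cut-off the known outcomes of recent conceptions are mostly early losses. Illustration (assumed): 15% of pregnancies lost at 10 weeks (0.19 years), the rest delivering at 0.75 years, conceptions even.
- Cut-off 0.9 years after start: losses 0.15 × (0.90 − 0.19) = 0.106; births 0.85 × (0.90 − 0.75) = 0.128; loss proportion 0.106/0.234 = 45%.
- Cut-off at 6.25 years: losses 0.15 × 6.06 = 0.909; births 0.85 × 5.5 = 4.675; loss proportion 0.909/5.584 = 16%.

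**The case against.** Much of the case on the other side is right.

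- A reader might infer that late infants and ongoing pregnancies sit in every denominator. The protocol does not say so. Incidence rates censor at study end, so late infants contribute only observed time. The proportion up to the extraction date names AESIs, SAEs and AEs. For malformations, growth, development, deaths and pregnancy outcomes no denominator is stated, and the SAP, not shown, may set one.
- A reader might also infer that late cases cannot be scored. They can in part. A late live birth yields birth status, prematurity, birth weight, size and malformations seen at birth, and growth or development at any age reached. A late conception can yield an early loss, a termination or maternal events. Only the part of each window after registry end is lost.
- Sections 9.5 and 9.9.4 mention extending the registry and finding other data. Infant-interval data are qualified by feasibility, and section 9.9.5 admits incomplete infant reporting.
- Table denominators are usually SAP matter, and the counts above rest on assumed conception timing.

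What remains is still more than missing detail. The extension is something to be considered, and the minimum named in section 9.9.4 is five years per participant, not completion of an infant's first year. No SAP can add follow-up after registry end or reword a primary objective. The crude proportion is a rule that the protocol itself states, and infant AEs are a primary variable (section 9.3.2.1.21) in a group that section 9.7.2 reports separately.

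**Conclusion.** The point holds in a limited form. The design does not secure the one-year infant window that the primary objective states, and the two accounts of registry end (section 9.1 and the synopsis) must be reconciled; the earlier date enlarges the gap. About 7 of 25 pregnancies would not be followable to one year under even conceptions with 6.25 years of collection, 6 to 8 over 7 to 5.5 years, and about 12 if conceptions rise linearly. These counts depend on the assumed conception pattern, nine months' gestation and no early losses.

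The bias in a crude infant AE or SAE proportion is modest under even births and constant hazard (10% shown as about 9.1%). It would be larger for events concentrated late in the first year. The documents do not support extending this bias to the incidence rates, nor presenting it as the stated treatment of the other pregnancy and infant outcomes.

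**What to change.** 1. **Objective and dates.** In section 8.2, the synopsis and Table 1 footnote h, state the window as running to the first birthday, or to registry end for infants born less than 12 months before it. Reconcile the registry end date between section 9.1 and the synopsis.
2. **Infant proportions (section 9.7.1, final and every interim report).** Base each age-specific proportion (3, 6, 9, 12 months) on infants born at least that long before the data cut-off, or use a time-to-event estimate censored at the cut-off.
3. **Pregnancy-outcome proportions (section 9.7.1).** Base them on pregnancies whose expected delivery date falls before the cut-off, whatever the date of the actual outcome. List ongoing pregnancies, and early outcomes of later conceptions, separately.

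The cost is wording and table specifications, with fewer infants and pregnancies in the restricted tables. Following late infants beyond registry end would keep the objective as it stands, but would need agreement with the registry.
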